11.2 Assessments performed only at screening/baseline

11.2.1 Demographics

The following demographic data will be recorded:

- Age: date of birth (or only year and month of birth as applicable according to local legislation).
- Sex: female; male.
- Race: American Indian or Alaska native; Asian; black or African American; native Hawaiian or other Pacific islander; white; or other. If 'other' is selected as race, a further specification needs to be provided in the eCRF.
- Ethnic origin (self-reported by the subject): Hispanic or Latino; not Hispanic or Latino.

11.2.2 Medical history

Relevant past and concurrent medical history must be recorded:

- Skin disease history. All past and current skin disease history including but not limited to:
 - Alopecia
 - Vitiligo
 - Herpes simplex infection

- Atopy history
 - Duration of AD in years
 - Previous AD treatments
 - Asthma
 - Food allergy
 - Hay fever
 - Allergic conjunctivitis
 - Atopic keratoconjunctivitis
 - Eczema herpeticum
- Other medical and surgical history including concurrent diagnoses

For each condition, diagnosis, or surgical procedure, the start date and stop date will be recorded; it will also be recorded if the condition, diagnosis, or surgical procedure is ongoing.

Relevant medical history also includes diseases which are specifically listed as exclusion criteria and diseases for which specific treatments are listed as exclusion criteria.

11.2.3 Height and weight

The subject's height (without shoes) will be measured; the subject's weight (in indoor clothing and without shoes) will be measured.

11.2.4 Body surface area involvement

The total body surface area (BSA) affected by AD will be assessed by the investigator for each section of the body as component A of SCORAD (see Section 11.3.3) and will be reported as a percentage of all major body sections combined. The following body regions will be assessed (brackets show the highest possible score for each region): head and neck (9%), anterior trunk (18%), back (18%), upper limbs (18%), lower limbs (36%), and genitals (1%). The total BSA score will be assessed according to the schedule of trial procedures (Section 4).

11.2.5 Columbia-Suicide Severity Rating Scale

The C-SSRS is a rater-administered instrument used to assess the lifetime history and severity of suicidal ideation and suicidal behaviour through a series of simple, plain-language questions (24, 25). The C-SSRS must be completed at the screening visit to check that

exclusion criterion no. 24 does not apply. Further details on the assessment according to the C-SSRS are included in the efficacy assessment & C-SSRS manual.

11.3 Efficacy assessments

11.3.1 Investigator's Global Assessment

The IGA is an instrument used in clinical trials to rate the severity of the subject's global AD and is based on a 5-point scale ranging from 0 (clear) to 4 (severe) (Panel 7; 26). The IGA score will be assessed according to the schedule of trial procedures (Section 4). The assessment will be based on the condition of the disease at the time of evaluation and not in relation to the condition at a previous visit. The IGA is included in the efficacy assessment & C-SSRS manual.

Panel 7: Investigator's Global Assessment

Score	Disease severity	Standard IGA scale	IGA morphological descriptors
0	Clear	No inflammatory signs of atopic dermatitis	No erythema and no elevation (papulation/infiltration).
1	Almost clear	Just perceptible erythema, and just perceptible papulation/infiltration	Barely perceptible erythema and/or minimal lesion elevation (papulation/infiltration) that is not widespread.
2	Mild disease	Mild erythema and mild papulation/infiltration	Visibly detectable, light pink erythema and very slight elevation (papulation/infiltration).
3	Moderate disease	Moderate erythema and moderate papulation/infiltration	Dull red, clearly distinguishable erythema and clearly perceptible but not extensive elevation (papulation/infiltration).
4	Severe disease	Severe erythema and severe papulation/infiltration	Deep/dark red erythema, marked and extensive elevation (papulation/infiltration).

Abbreviations: IGA, Investigator's Global Assessment.

11.3.2 Eczema Area and Severity Index

The EASI is a validated measure used in clinical practice and clinical trials to assess the severity and extent of AD (27). The EASI score will be assessed according to the schedule of trial procedures (Section 4). The assessment will be based on the condition of the disease at the time of evaluation and not in relation to the condition at a previous visit. Details on the scoring of severity and extent of AD according to EASI are included in the efficacy assessment & C-SSRS manual.

The EASI is a composite index with scores ranging from 0 to 72, with higher values indicating more severe or more extensive condition. The index will be calculated as shown in [Panel 8](#). Briefly, the investigator will assess the severity of 4 AD disease characteristics (erythema, induration/papulation, excoriation, and lichenification) on the 4 body regions (head/neck, trunk, upper extremities, lower extremities); severity will be assessed according to the scale shown in [Panel 9](#). For each body region, a severity sum score will be calculated which will be multiplied by an area score ([Panel 9](#)) and by a weighting factor. The EASI score equals the sum of the scores obtained for each body region ([Panel 8](#)).

Panel 8: Calculation of the Eczema Area and Severity Index

Body region	Erythema	Induration/ papulation	Excoriation	Lichenification	Area score	Weighting factor	Score
Head/neck	(SS +	SS +	SS +	SS)	x AS	x 0.1	
Trunk	(SS +	SS +	SS +	SS)	x AS	x 0.3	
Upper extremities	(SS +	SS +	SS +	SS)	x AS	x 0.2	
Lower extremities	(SS +	SS +	SS +	SS)	x AS	x 0.4	
The EASI score is the sum of the 4 body region scores							(range 0-72)

Abbreviations: AS, area score; EASI, Eczema Area and Severity Index; SS, severity score. Modified from (28).

Panel 9: Eczema Area and Severity Index severity score scale and area score scale

Severity score scale	
0	None/absent
1	Mild
2	Moderate
3	Severe

Note: half-steps (0.5, 1.5, 2.5) are allowed.

Area score scale	
0	0% affected area
1	1% to 9% affected area
2	10% to 29% affected area
3	30% to 49% affected area
4	50% to 69% affected area
5	70% to 89% affected area
6	90% to 100% affected area

11.3.3 SCORing Atopic Dermatitis

The SCORAD is a validated tool to evaluate the extent and severity of AD lesions, along with subjective symptoms (28). The maximum total score is 103, with higher values indicating more severe disease. SCORAD will be assessed according to the schedule of trial procedures (Section 4).

The assessment will be based on the condition of the disease at the time of evaluation and not in relation to the condition at a previous visit. Whenever possible, SCORAD should be assessed by the same investigator at each visit to reduce inter-rater variability.

The assessment consists of 3 components: A = extent, B = intensity, and C = subjective symptoms.

Extent (A)

The extent of AD is assessed as a percentage of each defined body area and reported as the sum of all areas (maximum score = 100%)

Intensity (B)

The intensity of 6 specific symptoms of AD (erythema, oedema/papulation, oozing/crusting, excoriation, lichenification, and dryness) is assessed by the investigator on an average representative area using the following scale:

0	=	None/absent
1	=	Mild
2	=	Moderate
3	=	Severe

Note: dryness is evaluated on uninvolved areas.

The sum of intensity score of the 6 symptoms will be reported (maximum score = 18).

Subjective symptoms (C)

A subjective assessment of the average itch and sleeplessness over the last 3 days/nights is recorded for each symptom by the subject on a visual analogue scale, where 0 is no itch (or sleeplessness) and 10 is the worst imaginable itch (or sleeplessness), with a maximum possible score of 20.

The SCORAD is calculated as: $A/5+7B/2+C$

11.3.4 Patient-reported outcomes

All PROs included in this trial are included in the investigator trial file.

11.3.4.1 Eczema-related Sleep numeric rating scale

Subjects will rate how much their eczema interfered with their sleep the last night using an 11-point NRS (0 indicating that it ‘did not interfere’ and 10 indicating that it ‘completely interfered’). Subjects will complete the Eczema-related Sleep NRS as part of an eDiary each day in the morning from Week -2 (visit 2) until Week 26.

11.3.4.2 Worst Daily Pruritus numeric rating scale

Subjects will assess their worst itch severity over the past 24 hours using an 11-point NRS (‘Worst Daily Pruritus NRS’) with 0 indicating ‘no itch’ and 10 indicating ‘worst itch imaginable’. Subjects will complete the Worst Daily Pruritus NRS as part of an eDiary each day in the morning from Week -2 (visit 2) until Week 26.

11.3.4.3 Patient Days of Topical Treatment Use

Subjects will assess their use of topical AD treatment over the past 24 hours using a response scale (‘yes’, ‘no’). Subjects will complete the Patient Days of Topical Treatment Use as part of an eDiary each day in the morning from baseline (Week 0 [visit 3]) until Week 26.

11.3.4.4 SF-36

The SF-36 (version 2, Acute Recall) is a 36-item general health status assessment. Subjects will be asked to answer each question by selecting one of 3 to 6 categorical response options. The instrument instructions do not state a specific recall period; however, a recall period is defined within most items. The acute recall version, which asks subjects about the last week, will be used in this trial (30).

The SF-36 (version 2) yields scores for 8 health domains (physical functioning, role physical, bodily pain, general health, vitality, social functioning, role emotional, and mental health) and 2 psychometrically derived summary scores (a physical component summary and a mental component summary).

The SF-36 will be completed electronically on the device supplied to the trial site according to the schedule of trial procedures in Section 4.

11.3.4.5 Patient-Oriented Eczema Measure

The POEM is a validated questionnaire used to assess disease symptoms in atopic eczema patients in both clinical practice and clinical trials (31). The tool consists of 7 items each addressing a specific symptom (itching, sleep, bleeding, weeping, cracking, flaking, and dryness). Subject will score how often they have experienced each symptom over the previous week on a 5-point categorical response scale (0 = 'no days'; 1 = '1 to 2 days'; 2 = '3 to 4 days'; 3 = '5 to 6 days'; 4 = 'every day'). The total score is the sum of the 7 items (range: 0 to 28) and reflects disease-related morbidity; a high score is indicative of a worse disease severity. The POEM will be completed electronically on the device supplied to the trial site according to the schedule of trial procedures (Section 4).

11.3.4.6 Dermatology Life Quality Index

The DLQI is a validated questionnaire with content specific to those with dermatology conditions. It consists of 10 items addressing the subject's perception of the impact of their skin disease on different aspects of their HRQoL over the last week such as dermatology-related symptoms and feelings, daily activities, leisure, work or school, personal relationships, and the treatment (32). Each item is scored on a 4-point Likert scale (0 = 'not at all/not relevant'; 1 = 'a little'; 2 = 'a lot'; 3 = 'very much'). The total score is the sum of the 10 items (0 to 30); a high score is indicative of a poor HRQoL. The DLQI will be completed electronically on the device supplied to the trial site according to the schedule of trial procedures (Section 4).

11.3.4.7 EQ-5D-5L

The EQ-5D-5L is a standardised measure of health status developed by the EuroQoL group to provide a simple, generic measure of health for clinical and economic appraisal (33). The EQ-5D-5L is a self-administered questionnaire used to assess health status 'today' and is divided into 2 sections: The first section includes 5 dimensions (mobility, self-care, usual activity, pain/discomfort, and anxiety/depression); each dimension will be assessed by the subject using a 5-point scale ('no problems', 'slight problems', 'moderate problems', 'severe problems', and 'extreme problems'). The second section consists of a vertical visual analogue scale anchored at 0 ('the worst health you can imagine') and 100 ('the best health you can imagine'). The EQ-5D-5L will be completed electronically on the device supplied to the trial site according to the schedule of trial procedures (Section 4).

11.3.4.8 Hospital Anxiety and Depression Scale

The HADS is a Likert scale tool widely used to detect states of anxiety and depression in a general hospital setting (34). The tool consists of 14 items that assess the subject's anxiety (7 items) and depression (7 items) during the last week. Each question is scored from 0 to 3, with high scores indicating a poor state. The HADS will be completed electronically on the device supplied to the trial site according to the schedule of trial procedures (Section 4).

11.4 Safety assessments

11.4.1 Vital signs

Vital signs (resting blood pressure, pulse, and body temperature) must be assessed according to the schedule of trial procedures (Section 4). Vital signs will be measured in a supine or sitting position following at least 5 minutes of rest.

For the first 3 IMP dosing visits (i.e., Weeks 0, 2, and 4), subjects will be monitored after IMP administration for immediate drug reactions for a minimum of 30 minutes with vital signs taken at 30 minutes or until stable, whichever is later (Section 9.2.1).

If an abnormal vital sign at screening is considered to be clinically significant by the investigator, it will be at the discretion of the investigator if the subject should be randomised into the trial (respecting exclusion criterion no. 26).

In case of abnormal findings, the vital sign measurement can be repeated approximately 15 minutes later with subjects resting in a supine position to verify the first measurement. Should the repeated measurement result in a normal value, the measurement must be repeated once more. If the third measurement verifies the second (normal) value, the first measurement should be considered false. If the third measurement confirms the first measurement (abnormal), the second measurement should be considered false. Only the last value measured and considered correct will be recorded in the eCRF.

Reporting in eCRF

Vital signs and the date and time they were measured will be recorded in the eCRF; if vital signs were not assessed, a reason should be given. Clinically significant abnormal vital signs at the screening visit will be documented as medical history in the eCRF. At subsequent visits, any clinically significant deterioration of a pre-existing condition as well as any new clinically significant sign, symptom, or illness will be reported as an AE in accordance with Section 13.3.

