Appendix 5: Guidance for anaphylaxis diagnosis

Source: Sampson et al., 2006 (41)

The National Institute of Allergy and Infectious Diseases (NIAID) and Food Allergy and Anaphylaxis Network (FAAN) Guidance for Anaphylaxis Diagnosis define anaphylaxis as a serious allergic reaction that is rapid in onset and may cause death. They recognise 3 categories of anaphylaxis, with criteria designated to capture from 80% of cases (category 1) to >95% of all cases of anaphylaxis (for all 3 categories).

Clinical criteria for diagnosing anaphylaxis

Anaphylaxis is highly likely when any one of the following 3 criteria are fulfilled:

- 1) Acute onset of an illness (minutes to several hours) with involvement of the skin, mucosal tissue, or both (e.g., generalised hives, pruritus or flushing, swollen lips-tongue-uvula)

AND AT LEAST ONE OF THE FOLLOWING:

- Respiratory compromise (e.g., dyspnoea, wheeze-bronchospasm, stridor, reduced peak expiratory flow [PEF], hypoxemia)
 - Reduced blood pressure (BP) or associated symptoms of end-organ dysfunction (e.g., hypotonia [collapse], syncope, incontinence)
- 2) Two or more of the following that occur rapidly after exposure to a likely allergen for that patient (minutes to several hours):
 - Involvement of the skin-mucosal tissue (e.g., generalised hives, itch-flush, swollen lips-tongue-uvula)
 - Respiratory compromise (e.g., dyspnoea, wheeze-bronchospasm, stridor, reduced PEF, hypoxemia)
 - Reduced BP or associated symptoms (e.g., hypotonia [collapse], syncope, incontinence)
 - Persistent gastrointestinal symptoms (e.g., crampy abdominal pain, vomiting)
 - 3) Reduced BP after exposure to known allergen for that patient (minutes to several hours):
 - Infants and children: low systolic BP (age specific) or greater than 30% decrease in systolic BP

Adults: systolic BP of less than 90 mm Hg or greater than 30% decrease from that person's baseline.

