## 6.7.2 Vital signs

Vital signs will be summarised and listed.

For the summary tables of vital signs by visit, the last pre-dose vital sign assessment will be presented. If no dosing occurs at a visit, the last assessment recorded at the visit will be presented.

For the first 3 IMP dosing visits, subjects will be monitored after IMP administration for immediate drug reactions for a minimum of 30 minutes with vital signs taken every 30 minutes or until stable, these measurements will be listed.

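### The repeat-and-discard rule for vital signs in Protocol 11.4.1 is not limited to screening or pre-dose readings, so an abnormal post-injection value can drop out of the eCRF and the SAP listing

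*Protocol*

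**What the plan says.** Protocol 11.4.1 does two things in one section. It sets post-injection monitoring at the first three dosing visits (Weeks 0, 2 and 4): "subjects will be monitored after IMP administration for immediate drug reactions for a minimum of 30 minutes". It also gives a repeat procedure for any abnormal vital sign: "In case of abnormal findings, the vital sign measurement can be repeated approximately 15 minutes later with subjects resting in a supine position". The procedure continues: "Should the repeated measurement result in a normal value, the measurement must be repeated once more". Then: "If the third measurement verifies the second (normal) value, the first measurement should be considered false". If instead the third reading is abnormal, the second is the one set aside. The recording rule is: "Only the last value measured and considered correct will be recorded in the eCRF".

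Four other statements bear on post-dose readings:

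- Protocol 5.6 gives the purpose of post-dose monitoring as a precaution against hypersensitivity reactions.
- Protocol 9.2.1 has the post-dose vital signs documented in the eCRF and says nothing about repeats.
- Panel 2 footnote 5 describes readings every 30 minutes or until stable.
- SAP 6.7.2 describes the same series and ends: "until stable, these measurements will be listed". For the by-visit summaries at dosing visits, it uses the last pre-dose value.

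**The concern.** A two-of-three rule suits a resting screening value, where the question is whether a single odd reading was an artefact. After an injection the question is different: did something happen and then pass? A brief real change and a measurement error produce the same sequence (abnormal, normal, normal), and the rule always settles on error.

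At stake is whether the post-dose vital-signs data can be trusted for the purpose given in Section 5.6. If sites apply the rule, a listing free of abnormal values could mean that none occurred, or that some occurred, recovered and were left out. A reader of the listing could not tell which.

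**Working it through.** No sample size, power or error-rate figure is involved, so this is a check of the text.

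**Step 1: scope.** The trigger in 11.4.1 is an abnormal finding, with no limit by visit or by timing relative to dose. The paragraph before it concerns abnormal values at screening, but the repeat paragraph does not carry that limit over. As worded, it reaches post-injection readings. No sentence in either document says that it does or does not.

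**Step 2: what the rule keeps.** After a first abnormal reading (A), with N for normal:

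| Sequence | Effect of 11.4.1 | Value in the eCRF |
|---|---|---|
| A, no repeat | Rule not used | A |
| A, A | Not spelled out; the last value is A | A |
| A, N, A | Second reading set aside | A |
| A, N, N | First reading set aside | N |

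The abnormality disappears only on the last path. On every path with a repeat, a single value is kept, so a timed series is not preserved.

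**Step 3: timing.** Take a first post-dose reading at 30 minutes. The repeat falls at about 30 + 15 = 45 minutes. No interval is given for the third reading; assuming another 15 minutes, it falls at about 60 minutes. A real change present at 30 minutes and gone by 45 follows the path A, N, N, and so does a faulty reading at 30 minutes. Nothing in the rule separates the two.

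**Step 4: from the eCRF to the report.** On that path the abnormal value is not in the eCRF, so it cannot be in the SAP 6.7.2 listing. It cannot appear in the by-visit summaries either, because at dosing visits these use the last pre-dose value. The listing is therefore the only planned output in which the value could have appeared.

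**Step 5: fit with the other sections.**

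| Place | Post-dose readings | Values kept |
|---|---|---|
| Protocol 9.2.1 | At 30 minutes or until stable | Documented in the eCRF |
| Protocol 11.4.1, monitoring paragraph | At 30 minutes or until stable | Not stated |
| Protocol 11.4.1, repeat paragraph | Repeat at about 15 minutes if abnormal | One: the last considered correct |
| Panel 2 footnote 5 | Every 30 minutes or until stable | Not stated |
| SAP 6.7.2 | Every 30 minutes or until stable | The measurements are listed |

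Monitoring until stable implies a series that includes the unstable readings. A rule that keeps one value does not fit it. The documents also disagree on whether the reading is at 30 minutes or every 30 minutes.

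**The case against.** The strongest reply is that the rule removes a number, not an event. Section 11.4.1 itself requires any new clinically significant sign, symptom or illness after screening to be reported as an adverse event. Section 13.2 has the investigator record observed changes that the subject does not report, and Appendix 1 counts an unintended sign as an adverse event even without symptoms. All of this stands. A reader might infer that reactions are erased, or that a symptom-free fall in pressure leaves no trace in the database; the documents do not support either. What remains is narrower. The safeguard depends on the investigator judging the reading clinically significant, while the same section says to consider that reading false.

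Second, the repeat is optional, and without it the abnormal value stands. That is correct, and it limits how often the problem can arise.

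Third, the post-injection instructions are specific and could be read as overriding the general repeat rule. This is a reasonable reading, but no sentence says so, and a site could equally follow the general rule.

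Three further inferences are tempting and should not be drawn:

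- **Anaphylaxis criteria.** Appendix 5 includes "systolic BP of less than 90 mm Hg or greater than 30% decrease" for adults, but under its third criterion, which requires exposure to an allergen already known for that patient. Exclusion criterion 14 removes subjects with known or suspected allergy to a component of the product. Under the other two criteria, reduced pressure counts only alongside other organ involvement. An isolated, recovered fall would not ordinarily qualify.
- **Number of readings lost.** 250 subjects × 3 visits = 750 monitored occasions at most, in both arms together. That counts occasions on which the rule could be used. It does not measure loss.
- **Position.** The general rule is "Vital signs will be measured in a supine or sitting position following at least 5 minutes of rest", whereas the repeat is supine. One might argue that a supine repeat cannot verify a seated reading. The rationale in the Amendment 1 history judged the effect of position insignificant, and the documents give no figure against that. The point here does not rest on it.

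**Conclusion.** The concern holds as a gap in scope and a conflict over recording. As worded, 11.4.1 lets an abnormal post-injection reading that is repeated and followed by two normal readings be replaced in the eCRF by a normal value, and so be absent from the SAP listing.

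The conclusion assumes that a site applies the general rule after injection, that it chooses to repeat, and that the change has resolved by the repeat. The documents do not show how often these coincide, so no number can be attached. No efficacy endpoint or estimand is affected; the effect is on the completeness of the post-dose safety data. It is worth correcting because the monitoring exists to detect short-lived changes and the correction is cheap.

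**What to change.** 1. In Protocol 11.4.1, state that the discard rule does not apply to readings taken after injection.
2. Record every post-dose value in the eCRF with its time and the subject's position.
3. In SAP 6.7.2, state that the listing contains all post-dose values, including those followed by a normal repeat.
4. Reconcile the reading at 30 minutes (Protocol 9.2.1 and 11.4.1) with the reading every 30 minutes (Panel 2 footnote 5 and SAP 6.7.2), so that the schedule, the text and the listing describe the same series.

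If these visits are already complete, check site source records for repeated readings at Weeks 0, 2 and 4, where they were kept, or state the limitation in the clinical trial report.

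The cost is repeat rows on the vital-signs eCRF page, a few sentences, and a slightly longer listing that will include some true measurement errors.
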